In this health-related research, the researchers first applied to health research ethics committees for permissions and once the permissions are taken, then the researchers identified the sample or user groups, through seminars at the Gjøvik hospital, using social media, etc. The researchers made sure that the user consent is received, the participation in our studies are voluntary and their participation can be ended any time by the user without any penalties for the user. Also, the Clinical Trials took place at The Psychiatry OPD of the Guru Tegh Bahadur Hospital of The University of Delhi.

Figure 4: The software detects the pupil, after detection it determines the focus point of gaze to control the virtual interaction

Hypothesis:

- (i) The new novel developed technology Intelligent Virtual Reality Therapy System (IVRTS) is more effective in reducing symptoms of Phobia and Anxiety as compared to Mindfulness Meditation and Cognitive Behavior Therapy Groups.
- (ii) The novel IVRTS Group scores significantly lower on both Hamilton Anxiety Inventory (HAM-A) and Subjective Units of Dysfunction Scale (SUDS) compared to all three, The Control Group, The Mindfulness Group Cognitive Behavior Therapy (CBT) Group.
- (iii) The Novel IVRTS Group scores significantly higher on WHO Quality of Life Scale (WHO QOL BREF) compared to all three, The Control Group, The Mindfulness Meditation Group and The CBT Group.
- (iv) The new technology proves to be effective and a steppingstone towards a newer era in the treatment of Mental Health issues using Mental healthcare engineering.

Sample

The Clinical Trials were carried out on 500 adults with Acrophobia which is fear of heights co-morbid with Generalized Anxiety. The sample for the study was recruited from the patients/subjects attending the adult psychiatric OPD of the department of Psychiatry GTB Hospital of The University of Delhi and fulfilling the

ICD-10 diagnostic criteria for assessment of Acrophobia and generalized anxiety. The study was conducted on an initial 500 subjects attending the psychiatric OPD of the department of Psychiatry GTB Hospital of the University of Delhi. The subjects were equally and randomly assigned to three groups namely; Novel Intelligent Virtual Reality System (IVRTS) Group (n=125), Mindfulness Meditation Group (n=125), Cognitive Behavior Therapy (CBT) Group (n=125) and The Control Group (n=125).

[figure not shown]

Figure 5: Consort Diagram

Inclusion Criteria

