The Inclusion criteria included patients visiting the Psychiatry OPD of University College of Medical Sciences of the University of Delhi and the attached GTB Hospital.

Furthermore, those patients were selected who reported fear of heights and scored mild, moderate and Severe anxiety as assessed on Hamilton Anxiety Inventory. The patients were in the age group between 18 to 60 years of age.

Exclusion Criteria

Patients who had any Psychotic disorder or symptoms co-morbid were not selected for the study. Furthermore, patients below 18 years of age and aver 60 years of age were also not selected for the program

Registration

All procedures involving human subjects/patients were jointly approved by The University College of Medical Sciences (University of Delhi) and Delhi Psychiatry Society Ethics Committee registration. Registration number 3/1/333011/HRD. The patients were first recruited on 5th February 2018 for the project.

Procedure and Approaches

To achieve the stated objective, a two-fold approach comprising of qualitative and quantitative analysis was undertaken. A 7-week intervention course was designed for each subject to reduce symptoms and enhance quality of life as well as to establish clinical efficacy. The intervention was conducted on a sample of 500 patients diagnosed with Acrophobia co-morbid with generalized anxiety who underwent the intervention at The GTB hospital of The University of Delhi, for a total of 3500 sessions, ranging up to 5250 Hours over a period of 2 years. Written informed consent was obtained from all participants. The authors assert that all procedures contributing to this work comply with the ethical standards of the relevant national and institutional committees on human experimentation and with the Helsinki Declaration of 1975, as revised in 2008. All procedures involving human subjects/patients were jointly approved by The University College of Medical Sciences (University of Delhi) and Delhi Psychiatry Society Ethics Committee registration. Registration number 3/1/333011/HRD. Further study carried out A-B-A research design which mainly involved establishing a baseline condition, introducing an experimental treatment and then returning to the baseline. The subjects

completed standardized self-report measures of Hamilton Anxiety Inventory (HAM-A),
Subjective Units of Dysfunction (SUDS) and WHO Quality of Life - BREF Questionnaire

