(QOL-BREF) at baseline, after seven intervention sessions post assessments on the same scales were repeated to assess the efficacy.

The Therapeutic Software of IVRTS

The researchers developed four different technological approaches to develop the Psychotherapeutic Software. (1) Since phobias are known to stem from mental images of situations or objects which an individual has learned to be fearful of. Thus, the most effective way to treat them, then, would be to alter these anxietyprovoking images with the help of graded exposure of an image of a situation or object which induces maximum pleasure and positive emotions within the individual. This was achieved with the help of development of motion sensors to detect the wrist movements of the subjects, which aided in achieving the desired goal of stimulating the pleasure-inducing stimulus to reduce anxiety. This was accompanied by monitoring the subject's physiological parameters through body biofeedback and fNIRS depicting the changes brought about by VR therapy and keeping the record of the same. (2) When an individual encountered a fearful stimulus, certain kind of neurotransmitters are released in the brain and over time, the body and mind of the individual learn to associate the release of these neurotransmitters with fear. This association was altered by flooding the individual's mind with pleasurable memories in the form of positive images using Virtual Reality Technology and thereby replacing unpleasant memories attached to the neurotransmitter release with pleasant memories. It was followed by guided instruction from the IVRTS device along the concept of 'Whole Brain Thinking' wherein all the five sense organs are used to exercise all the parts of the brain to take advantage of a wide spectrum of thinking. (3) As described in Figure 1, Cognitive Behavioral Therapy

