(CBT) states that it is not the situation itself but the thought associated with the situation (stimulus) which makes an individual fearful. Altering this thought and the emotions related to it is hence helpful in treating phobias. This was achieved by integrating an automated intelligent Cognitive Behavior Therapy software program with the VR device. 4) Finally, the researchers used Mindfulness Relaxation as a treatment for phobia. This was implemented by making the subject face the anxiety-provoking situation with the help of VR equipment and simultaneously working on reducing the anxiety emotions with the help of guided mindfulness meditation accompanied by meditation music, along with the developed automated intelligent therapy software interface. This methodology was intended to put the subject in a peaceful state of mind, detaching them from negative thoughts and fears, working on the principle that anxiety and relaxation cannot coexist.

[figure not shown]

Figure 6: Understanding CBT Software

Project Plan

[figure not shown]

Figure 7: Project plan

01/08/2020

OUTCOMES AND RESULTS

The quantitative and qualitative results were analyzed with the appropriate statistical and analytical tools. Various statistical modalities were used to establish efficacy, efficiency and the frequencies evaluated. Paired sample t- test were conducted in this study to assess the statistical significance of the interventions.

Independent sample t-test and ANOVA were tested in the data. Correlation analysis was also performed, The association between two categorical variables is enumerated by Chi-square test.

Scale	Mindfulness (n=118)		Control (n=125)		t-	F-	p-value
	Pre	Post	Pre	Post	value	value	
	Mean±SD		Mean±SD				
HAMA	32.86±5.76	19.62±4.24	33.70±6.08	28.00±6.49	8.350	2.327	0.000
SUDS	8.24±0.95	5.69±1.04	8.27±1.11	6.03±1.29	1.228	0.178	0.225
QOL	73.86±7.73	84.10±5.19	75.47±5.44	82.53±4.85	-2.229	6.242	0.030

Table 1: Mean comparison between Mindfulness Meditation group (n=118) and control group (n=125)

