Table 1 represents the mean comparison between Mindfulness group and the Control Group of respondents while before and after intervention. On The Hamilton Anxiety scale, most of the respondents in The Mindfulness Group had very severe condition while before intervention with mean score (M=32.86), but it reduced to mean score (M=19.62). While in the control group, most of the respondents had very severe condition while before intervention with mean score (M=33.70) and moderate to severe condition while after intervention with mean score (M=28.00). The obtained t-value and p-value for Hamilton scale are 8.350 and 0.000 respectively. Here, p-value is less than 0.01; it indicates that there is a statistically significant difference between mindfulness and control group of respondents based on Hamilton scale. Similarly when considered the Subjective Unites of Dysfunction Scale (SUDS), most of the respondents of The Mindfulness Group, felt 'Freaking out' while before intervention with mean score (M=8.24) and 'Moderately upset' while after

intervention with mean score (M=5.69). But in the control group, most of the respondents felt 'Freaking out' while before intervention with mean score (M=8.27) and 'bad' while after intervention with mean score (M=6.03). The obtained t-value and p-value for SUDS are 1.228 and 0.225 respectively. Here, p-value is greater than 0.05, and indicated that there is no significant difference between mindfulness and control group of respondents based on SUDS. Similarly, obtained t-value and p-value for Quality of life are -2.229 and 0.030. Here p-value is less than 0.05; and shows a statistically significant difference between Mindfulness and Control group in relation to WHO Quality of life (QOL - BREF) scale of respondents.

	CBT (n=106)		Control (n=125)				
Scale	Pre	Post	Pre	Post	t-	F-	p-
	Mean±SD		Mean±SD		value	value	value
HAMA	32.52±5.24	21.03±4.29	33.70±6.08	28.00±6.49	6.905	2.312	0.000
SUDS	8.24±0.98	5.34±1.14	8.27±1.11	6.03±1.29	2.366	0.344	0.021
QOL	73.62±5.23	83.28±5.06	75.47±5.44	82.53±4.85	-2.714	0.002	0.009

Table 1: Mean comparison between CBT group (n=106) and Control group (n=125)

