Table 2 presents the mean comparison between CBT group and control group of respondents before and after intervention. On the Hamilton Anxiety scale, most of the respondents of the CBT Group had very severe condition while before intervention with mean score (M=32.52), which reduced to mild to moderate severe after the intervention witj mean score (M=21.03). In control group, most of the respondents were in very severe condition while before intervention with mean score (M=33.70) and improved to moderate to severe condition after the intervention with mean (M=28.00). The obtained t-value and p-value for Hamilton scale are 6.905 and 0.000 respectively. Here, p-value is less than 0.01, it indicates a statistically significant difference between CBT and control group of respondents based on Hamilton Anxiety scale. Similarly, on the SUDS of respondents, most of the respondents felt 'Freaking out' while before intervention with mean (M=8.24) and

'Moderately upset' after the intervention with mean (M=5.34). But in the control group, most of the respondents felt 'Freaking out' before the intervention with mean (M=8.27) and felt 'bad' after intervention with mean (M=6.03). The obtained t-value and p-value for SUDS is 2.366 and 0.021 respectively. Here, p-value is less than 0.05, indicating a statistically significant difference between CBT and control group of respondents based on SUDS. Similarly obtained t-value and p-value for Quality of life are -2.714 and 0.009. Here p-value is less than 0.01; indicating a statistically significant difference between CBT and Control group in relation to The WHO Quality of life (QOL- BREF) scale of respondents.

	Novel IVRTS (n=115)		Control (n=125)		t-	F-	
Scale	Pre	Post	Pre	Post	_		p- value
	Mean±SD		Mean±SD		value	value	value
HAMA	28.60±8.45	11.10±4.03	33.70 ± 6.08	28.00±6.49	8.088	23.503	0.000
SUDS	8.10±1.56	3.73 ± 1.23	8.27±1.11	6.03 ± 1.29	7.503	2.315	0.000
QOL	72.87±6.21	87.07±3.79	75.47±5.44	82.53±4.85	-6.313	4.519	0.000

Table 3: Mean comparison between IVRTS (n=115) and Control group (n=125)

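### The post assessment is tied to finishing seven sessions, with no fixed time from baseline and no assessment for patients who stop; all 36 losses are in the active arms

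*Combined protocol and SAP*

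**What the plan says.** The combined protocol and SAP gives one rule for the outcome assessment, at the end of Procedure and Approaches. HAM-A, SUDS and WHOQOL-BREF are taken at baseline, and then "after seven intervention sessions post assessments on the same scales were repeated to assess the efficacy". The same section gives the length of the course: "A 7-week intervention course was designed for each subject to reduce symptoms and enhance quality of life". It does not say that week 7 is the assessment time, and it gives no visit window or make-up rule.

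Technology Components and Clinical Trials lets a participant stop at any time without penalty. Neither it nor any other readable section says whether someone who stops is still assessed.

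On who was treated, Procedure and Approaches says: "The intervention was conducted on a sample of 500 patients diagnosed with Acrophobia co-morbid with generalized anxiety who underwent the intervention", "for a total of 3500 sessions, ranging up to 5250 Hours over a period of 2 years". The Sample section allocates 125 patients to each of four arms. What Control received, and when it was reassessed, is not described, although the results tables give Control post scores for all 125.

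**The concern.** A session count measures treatment received after randomisation. If it triggers the outcome assessment, it decides both when the outcome is measured and in whom. A patient who postpones sessions is measured later, and a patient who stops after, say, five sessions never reaches the trigger.

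The second consequence is the more serious. Patients who do not finish a therapy are unlikely to resemble those who do, so an active arm made up of completers is no longer the arm that was randomised. If the losses differ between arms, part of the difference from Control may reflect selection. The problem arises at data collection: choosing an intention-to-treat analysis set afterwards does not supply scores that were never taken.

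**Working it through.** **1. The plan's session total.** 500 patients × 7 sessions = 3500, which reproduces the stated figure exactly, and 5250 / 3500 = 1.5 hours per session. Two alternatives do not reproduce it: the three active arms alone give 375 × 7 = 2625, and the analysed patients alone give 464 × 7 = 3248. Taken literally, the total therefore includes 125 × 7 = 875 Control sessions and leaves no room for a missed session in any arm.

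**2. Who has a post score.** Allocation is from the Sample section; analysed numbers are from the table captions in Outcomes and Results.

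| Arm | Allocated | Analysed | Missing |
|---|---|---|---|
| Mindfulness | 125 | 118 | 7 (5.6%) |
| CBT | 125 | 106 | 19 (15.2%) |
| IVRTS | 125 | 115 | 10 (8.0%) |
| Control | 125 | 125 | 0 |

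The missing total is 7 + 19 + 10 = 36, or 36/375 = 9.6% in the active arms against 0/125 in Control (Fisher exact p = 0.00003). Across four arms, chi-square is 22.3 on 3 df (p = 0.00006). CBT against IVRTS alone gives Fisher p = 0.11.

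This is the pattern that a completion-triggered assessment would produce. It also conflicts with a literal reading of step 1, in which nobody missed a session.

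**3. How much the losses could matter.** As an illustration, assume every missing patient stayed at the printed baseline mean of the arm:

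revised post mean = (analysed n × post mean + missing n × baseline mean) / 125.

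For CBT on QOL: (106 × 83.28 + 19 × 73.62) / 125 = 10226.46 / 125 = 81.81. Control is 82.53, so the difference moves from 83.28 − 82.53 = +0.75 to 81.81 − 82.53 = −0.72.

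The same formula gives these post-mean differences from Control, as reported and then revised:

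| Arm | HAM-A | SUDS | QOL |
|---|---|---|---|
| Mindfulness | −8.38 → −7.64 | −0.34 → −0.20 | +1.57 → +1.00 |
| CBT | −6.97 → −5.22 | −0.69 → −0.25 | +0.75 → −0.72 |
| IVRTS | −16.90 → −15.50 | −2.30 → −1.95 | +4.54 → +3.40 |

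Only CBT on QOL changes sign.

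**4. The same check on change from baseline.** Control starts higher on QOL (75.47, against 73.62 in CBT and 73.86 in Mindfulness), so post means understate the gaps. Control gains 82.53 − 75.47 = 7.06, CBT 83.28 − 73.62 = 9.66 and Mindfulness 84.10 − 73.86 = 10.24. The excess over Control is 2.60 for CBT and 3.18 for Mindfulness. With the 19 missing CBT patients given no change, the CBT gain becomes 9.66 × 106/125 = 8.19 and the excess 8.19 − 7.06 = +1.13. It more than halves but keeps its sign.

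**The case against.** **The natural reading is an assessment at about week 7.** Seven sessions in a 7-week course suggest an end-of-course visit, and the sentence describes what was done; it does not expressly exclude early stoppers. This stands in part. There is a nominal common time, but the text does not fix it and makes no provision for those who stop.

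**Control may have had the same trigger.** A reader might infer that Control had no equivalent time point. The documents do not support that: they say all 500 patients underwent the intervention, and their session total implies seven for each Control patient. The supportable statement is that Control's content and timing are undefined and do not sit easily with that total.

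**Nothing shows late assessment.** A reader might also infer that delay in the active arms explains the weaker contrasts, because Control itself improves. No dates or individual session counts are reported, and no length of delay can be sourced. Even if Control's change were linear over 7 weeks (an assumption), HAM-A would drift by 5.70 / 7 = 0.81 points a week. Producing the IVRTS difference of 16.90 would then take about 21 weeks. On change scores the gap is (28.60 − 11.10) − 5.70 = 11.80, or about 14 to 15 weeks. Delay is no credible explanation for that result. This objection stands, and no magnitude is claimed for delay.

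**The losses may have other causes.** No reason for them is given, and the Consort diagram and project plan (Figures 5 and 7) are not shown; they may hold reasons or a schedule. This stands: the link from rule to losses is an inference.

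**The CBT sign change concerns a contrast already weak on post means.** From the tabulated SDs and numbers, 0.75 / √(5.06²/106 + 4.85²/125) = 0.75 / 0.656, so t is about 1.1, against a reported magnitude of 2.714 (p = 0.009). The reversal therefore does not directly overturn the reported test, whose basis is unclear. It does show how little that difference can bear.

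**Conclusion.** The concern holds in limited form. The stated trigger is a session count, with no fixed time from baseline and no provision in the readable text for patients who stop. Followed as written, it leaves non-completers without a post score, and the reported losses (36 of 375 in the active arms, none in Control) are consistent with that.

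The smaller contrasts are sensitive. Under the baseline-mean assumption, CBT minus Control on post QOL goes from +0.75 to −0.72, or from +2.60 to +1.13 on change. That assumption is an illustration, not an estimate, and it uses the printed baseline means, which may describe analysed patients only.

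A reader might infer that the superiority of IVRTS over Control is an artefact of the rule. The documents do not support this: its direction is unchanged on all three scales under the same assumption. The point should be corrected, but it does not by itself overturn the main comparison. Separately, Control's undefined content and timing, the 3500-session total and the 36 losses must be reconciled.

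**What to change.** **For any further enrolment**, replace the rule with: HAM-A, SUDS and WHOQOL-BREF are repeated in all four arms at a common time from baseline (nominally week 7, with a stated window), whatever number of sessions was attended. Describe Control's content and its assessment time.

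**For patients already treated**, leave the procedure text as the record of what was done; rewriting it as a week-7 rule would misdescribe the trial. Instead:

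- Report by arm, where recorded, days from baseline to post assessment, sessions attended and reasons for the 36 losses.
- Say whether the 3500 sessions are planned or delivered, and whether they include Control.
- Include any post score that exists, regardless of sessions attended.
- Repeat each between-arm comparison on all 500 randomised patients with a stated missing-data method, and add a baseline-carried-forward sensitivity analysis.

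Do not simply restrict the comparisons to assessments made near week 7. That conditions on attendance after randomisation and recovers none of the 36 missing patients.

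The cost is a short change to the procedure, one table and one re-analysis, provided dates and attendance were kept. For new patients there is also the work of assessing those who have stopped. Estimated effects may be somewhat smaller, because partly treated patients would count.

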Funding: No funding to report as of now. Funding by The Research Council of Norway is proposed after evaluation the developed prototype mentioned in this article.

Correspondence concerning this article should be addressed to [name]

IIIT Delhi University, [name].

Email: [contact]

ABSTRACT

Background: To take the existing VR technology to the next level, we developed a novel Intelligent Virtual Reality Therapy System (IVRTS). Aim: The objective of this project had three aspects: Namely, development of the novel IVRTS technology involving the development of a hardware device, development of Artificially Intelligent Psychotherapeutic software-interface and testing it's clinical efficacy. *Methods*: It used a two-phased methodology; Development of the novel technology and testing its Clinical Efficacy. After development of Novel IVRTS. A 7-week intervention was designed for each subject. The sample of 500 patients, meeting the criteria of Acrophobia and Anxiety, underwent the interventions at The GTB hospital (The University of Delhi), for a total 3500 sessions, ranging 5250 hours for over 2 years. The subjects were randomly divided into 4 groups: IVRTS Group, Mindfulness group, CBT group and Control Group. *Registration:* The ethics committee and clinical trial registration number is 3/1/333011/HRD. *Results*: The IVRTS group reported significant reduction in Acrophobic and Anxiety symptoms. The Pre and Post intervention, mean and SD reduced from 28.60±8.45 to 11.10±4.03 on HAMA; from 8.10±1.56 to 3.73±1.23 on SUDS and increased from 72.87±6.21 to 87.07±3.79 on WHO-QOL-BREF. It was also seen the mean comparison of reduction was significantly higher compared to the CBT and Mindfulness Groups. It also indicated enhanced Quality of Life (p < .001) compared to The Mindfulness Group and CBT Group. *Conclusion:* IVRTS decreased symptoms of Acrophobia and Anxiety, enhanced Quality of Life significantly than other treatment groups. Development of this technology is a land-mark innovation.

Key Words: Anxiety; Virtual Reality; Phobias; Treatment Intervention.

INTRODUCTION

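### The paired pre-post t-test named for judging the interventions cannot show efficacy, because the Control arm passes it too; the efficacy test and the abstract need baseline-adjusted between-arm differences

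*Combined protocol and SAP*

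**What the plan says.** The opening paragraph of OUTCOMES AND RESULTS states: "Paired sample t- test were conducted in this study to assess the statistical significance of the interventions". The next sentence adds: "Independent sample t-test and ANOVA were tested in the data". It does not tie those two tests to a hypothesis or a scale, and does not say that they adjust for the pre score.

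The Results part of the ABSTRACT opens with "The IVRTS group reported significant reduction in Acrophobic and Anxiety symptoms". It supports this with the IVRTS means alone: "28.60±8.45 to 11.10±4.03 on HAMA", "8.10±1.56 to 3.73±1.23 on SUDS", and a QOL rise from 72.87 to 87.07. It then claims superiority over CBT and Mindfulness, but gives no between-arm difference and no Control figures.

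Elsewhere the document reasons between arms. Hypothesis (ii) reads "The novel IVRTS Group scores significantly lower on both Hamilton Anxiety Inventory (HAM-A) and Subjective Units of Dysfunction Scale (SUDS") compared with each of the other three arms. Tables 1 to 3 set each active arm beside Control, for example "Table 3: Mean comparison between IVRTS (n=115) and Control group (n=125"). The text on Table 2 describes Control's own improvement: ("M=33.70) and improved to moderate to severe condition after the intervention with mean (M=28.00").

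**The concern.** The trial randomises to four arms, one of them a control. Change within one arm mixes any treatment effect with everything else that moves scores between two assessments, such as regression to the mean, repeat testing and the ordinary course of the condition. A paired t-test asks only whether the mean moved. If Control moves enough to pass, the test cannot separate an effective intervention from the comparison condition.

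The paired test is the only one that the text links to judging the interventions, and the abstract shows only within-arm changes. A reader of the abstract would take the full pre-post change as the effect of IVRTS and could not see how much of it also occurred in Control. The between-arm tests that are named leave a second gap. They are not stated to adjust for baseline, and the arms differ at baseline.

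**Working it through.** **Inputs.** Means, SDs and n are from Tables 1 and 3: Control n=125, IVRTS n=115, Mindfulness n=118. The pre-post correlation r is not given, so it is an assumption and a range is shown.

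**1. The document's own figures.** No paired t is printed, so there is none to reproduce. Table 3 prints IVRTS-versus-Control t of 8.088 (HAM-A), 7.503 (SUDS) and -6.313 (QOL). A pooled t on post scores from the same table gives 23.99, 14.11 and -8.03. A t on change scores matches only if r is about -0.60, -0.43 and -0.47, which is implausible for repeated scores. The printed t-values are therefore not reproduced at the stated n. The steps below use the printed means, SDs and n.

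**2. Paired test in Control.** SD of change = sqrt(s_pre² + s_post² - 2·r·s_pre·s_post), and t = mean change / (SD of change / sqrt(n)). The smallest possible t in absolute size is at r = -1, where the SD of change is s_pre + s_post. For HAM-A that is 6.08 + 6.49 = 12.57, the standard error is 12.57/sqrt(125) = 1.124, and t = -5.70/1.124 = -5.07.

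| Scale | Control pre to post | Change | t, r=-1 | t, r=0 | t, r=0.5 | t, r=0.9 |
|---|---|---|---|---|---|---|
| HAM-A | 33.70 to 28.00 | -5.70 | -5.07 | -7.17 | -10.12 | -22.45 |
| SUDS | 8.27 to 6.03 | -2.24 | -10.43 | -14.72 | -20.70 | -44.36 |
| QOL | 75.47 to 82.53 | +7.06 | 7.67 | 10.83 | 15.27 | 33.28 |

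Every p is below 0.00001. No value of the missing correlation makes Control fail.

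**3. Share of the IVRTS change also seen in Control.** HAM-A 5.70/17.50 = 33%; SUDS 2.24/4.37 = 51%; QOL 7.06/14.20 = 50%.

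**4. Does the choice of test matter?** Mindfulness SUDS went from 8.24 (SD 0.95) to 5.69 (SD 1.04), a change of -2.55. At r = -1 the SD of change is 1.99, and t = -2.55/(1.99/sqrt(118)) = -13.9; at r = 0 it is about -20. The paired rule would call Mindfulness effective on SUDS. Table 1 compares the same arm with Control, prints t=1.228 and p=0.225, and the text reads this as no difference. This printed value is not reproduced either. A pooled post-score t from the summaries is (6.03 - 5.69)/(1.175·sqrt(1/118 + 1/125)) = 2.25, with p about 0.025. The reversal of conclusion therefore rests on the document's own p-value. The gap between about 14 and about 1 or 2 does not.

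**5. Baseline, IVRTS against Control (pooled t).**
- HAM-A: 28.60 vs 33.70, pooled SD 7.31, standard error 0.945, |t| = 5.10/0.945 = 5.4.
- QOL: 72.87 vs 75.47, pooled SD 5.82, standard error 0.752, |t| = 2.60/0.752 = 3.5.

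**6. ANCOVA rebuilt from the summaries.** The common slope is b = r·Σ(n-1)·s_pre·s_post / Σ(n-1)·s_pre², summed over the two arms. The adjusted difference is (post difference) - b·(pre difference). For HAM-A at r = 0.9, b = 0.621 and the difference is -16.90 - 0.621·(-5.10) = -13.73.

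| Scale | r=0 | r=0.5 | r=0.9 | IVRTS pre-post change in abstract |
|---|---|---|---|---|
| HAM-A | -16.90 | -15.14 | -13.73 | -17.50 |
| SUDS | -2.30 | -2.22 | -2.16 | -4.37 |
| QOL | +4.54 | +5.50 | +6.27 | +14.20 |

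All have p<0.001 at the stated n.

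**The case against.** The strongest reply is that the efficacy claim does not rest on paired tests. The sentence after the paired-test statement names independent t-tests and ANOVA, and hypotheses (i) to (iii) are between-arm. Tables 1 to 3 give a comparison with Control for each scale, the text reads each as a between-group difference, and no paired statistic is printed. Control's improvement is shown in the tables and described in words. The abstract does not say which test lies behind its significant reduction, and it goes on to claim superiority over CBT and Mindfulness. On the printed summaries the IVRTS-Control contrast stays significant after correction. All of this stands, and it limits the point to the method statement and the abstract.

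Three stronger readings are tempting but not supported:
- A reader might infer that an untreated arm recovered naturally and that this recovery was credited to IVRTS. The documents never call Control untreated and do not say what it received. The stated 3500 sessions equal 500 × 7, a count that includes Control's 125 patients. Control's change cannot be labelled natural improvement.
- A reader might subtract the changes and take 11.80, 2.13 and 7.14 as the corrected effects. Those are differences in change. With unequal baselines they are not what ANCOVA gives: on the rebuilt figures the adjusted HAM-A effect is larger than 11.80 and the adjusted QOL effect is smaller than 7.14.
- A reader might infer that the advantage of IVRTS disappears. On the printed summaries it does not.

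**Conclusion.** The concern holds in limited form. The one test that the text ties to judging the interventions is passed by the Control arm on all three scales at any pre-post correlation, so it cannot serve as evidence of efficacy. The abstract's only numerical effects are within-arm changes, of which a third (HAM-A) to about a half (SUDS and QOL) also occurred in Control.

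A baseline-adjusted contrast with Control would be 78% to 97% of the headline change for HAM-A (13.73/17.50 to 16.90/17.50), 49% to 53% for SUDS (2.16/4.37 to 2.30/4.37) and 32% to 44% for QOL (4.54/14.20 to 6.27/14.20). The size and basis of the claim change; its direction does not.

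The result for Control needs only the printed means, SDs and n. The adjusted differences also assume r between 0 and 0.9, equal in both arms, and a common slope. Because the printed t-values do not follow from the same summaries, the final estimates and intervals must come from the raw data.

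**What to change.** - In OUTCOMES AND RESULTS, name as the efficacy test for each scale an ANCOVA of post score on arm with pre score as covariate. Keep paired pre-post results as description only.
- In the abstract, report the adjusted IVRTS-minus-comparator differences with 95% confidence intervals from the raw data. If the pre and post means stay, show Control's beside them and do not present within-arm change as evidence of effect.
- State what the Control arm received, so that the contrast can be interpreted.

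The cost is a re-analysis of data already held, some rewording, and smaller headline effects, most visibly for SUDS and QOL. No new data are needed.
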